1 PROTOCOL SUMMARY

1.1 SYNOPSIS

Title:	Pain Response Evaluation of a Combined Intervention to Cope Effectively (PRECICE)
Grant Number:	1UG3NR019196-01
Study Description:	The purpose of this research is to determine if the combination of non-opioid medication (duloxetine) and web-based pain-coping skills training (PCST), with or without health care professional support, is beneficial for individuals with chronic musculoskeletal pain (CMP).
Objectives[*]:	The objective of this study is to conduct a 24-week randomized clinical trial of primary care patients with CMP. 280 participants will be randomized to one of three treatments: (1) combination treatment [duloxetine + web-based cognitive behavioral therapy CBT] with health care professional support, (2) combination treatment without health care professional support, and (3) duloxetine monotherapy.
Endpoints[*]:	
Primary Endpoint: Brief Pain Inventory (BPI)-Global Pain Severity (GPS)
 
Subgroup Analyses: We will conduct subgroup analysis using linear mixed effects models (LMMs) to test the interactions between intervention arm (with and without health care professional support vs. monotherapy) and baseline characteristics.
 
Secondary Endpoints: The secondary outcomes will include the two individual components of the BPI GPS: BPI pain severity and BPI pain interference.
 
Tertiary Endpoints:
 
1. Global Rating of Change (GRC)2. PROMIS pain intensity3. PROMIS pain interference4. Chronic Pain Coping Inventory (CPCI) 
Exploratory Endpoints:
 
1. Generalized Anxiety Disorder 7-item scale (GAD-7)2. Patient Health Questionnaire 8-Item Depression Scale (PHQ-8)3. Pain catastrophizing scale (PCS)4. SF 36 physical function (SF 36)4. PROMIS Adult measures: physical function, fatigue, social health, sleep disturbance, pain behavior5. Opioid Morphine Equivalent (OME)6. Health care service utilization7. PHQ Anxiety-Depression Scale (PHQ-ADS)8. Frequency of Practicing Pain Coping Skills9. Others. Medication use and co-intervention effect.

For a full description of these endpoints see section 8.1.

Study Population:

(1) patients at the primary care clinic with daily pain for 3 months or longer affecting the low back, neck, hip, knee or widespread pain; 2) at least moderate in BPI GPS, defined as a GPS score of 5 or greater^{1,2}; and (3) at least age 18 years old or older. ~~We are restricting our age criteria because of the risk of poly pharmacy from centrally acting medications in older adults.~~ All sexes who meet these criteria are eligible for the study. (n=280)

Phase^{*} or Stage:

Phase 4

**Description of
Sites/Facilities Enrolling
Participants:**

We will recruit participants from the 271 primary care clinics within the Atrium Health - Wake Forest (WF) Baptist Health System as well as surrounding providers outside of Atrium Health in North Carolina .

Description of Study Intervention/Experimental Manipulation: PRECICE is a 24-week randomized controlled clinical trial (RCT) of patients in the primary care clinics. During the study, participants will be randomized to one of three treatments: (1) [duloxetine + web-based CBT] with health care professional support, vs. (2) [duloxetine + web-based CBT] without health care professional support, vs. (3) duloxetine only.

Web-based Cognitive Behavioral Therapy (web-based CBT). The web-based CBT program is an automated program (i.e., users learn skills with interactive, personalized training without any therapist contact) that includes 8, 35- to 45-minute training sessions, each of which provides an educational rationale and training in cognitive or behavioral pain coping skill drawn from face-to-face CBT³.

Health care professional-delivered Motivational Interviewing (MI). The primary purpose of health care professional contact is to enhance participant's motivation to engage in web-based CBT by encouraging participant's continued use and practice of pain coping skills. Subjects randomized to the [duloxetine + web-based CBT] with health care professional support will receive 6 phone calls from a MI trained health care professional at week 3, 6, 10, 14, 18 and 22. Telephone sessions may run for 20 minutes on the average.

Duloxetine. We chose duloxetine as the first line drug because: (1) it has established efficacy for CMP and Food and Drug Administration (FDA) approval for that indication; and (2) it is available in generic form, which makes it more readily available. At study entry, all participants will receive duloxetine 30 mg once daily for one week; subjects who are able to tolerate 30 mg and do not have chronic kidney disease III (CKD-3) will increase to 60 mg once daily for 24 weeks. At week 25, participants will return to the research clinic for outcome assessments. At the last study visit (week 25), participants who would like to stop the medication, will be provided duloxetine 30 mg once daily for 7 days and medication treatment will then stop (tapering regimen). Subjects already taking 30 mg daily will stop dosing at their week 25 visit. Those who would like to continue duloxetine will be prescribed a 2-week supply of duloxetine and will be instructed to talk to their primary care provider (PCP). In addition, the investigator will send a Wake One message to the PCP to consider continuation of duloxetine.

Other treatments. The use of over-the-counter analgesic medications will be permitted and assessed to adjust for co-intervention differences between groups in the analyses.

For further details, see Section 6, Study Interventions or Experimental Manipulations.

Study Duration^{*}:

[figure not shown]
The estimated time from when the study opens to enrollment until completion of data collection is 45 months.

Participant Duration:

The time it will take for each individual participant to complete all study-related tasks is 25 weeks.

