7.3 LOST TO FOLLOW-UP

A participant will be considered lost to follow-up if he or she fails to return for one IPV and study staff are unable to contact the participant after at least 3 attempts.

The following actions must be taken if a participant fails to return to the clinic for a required study visit:

- The staff will attempt to contact the participant, reschedule the missed visit, counsel the participant on the importance of maintaining the assigned visit schedule and ascertain if the participant wishes to and/or should continue in the study.
- Study staff will utilize a participant provided alternate contact list, if necessary, to reach the participant.
- Before a participant is deemed lost to follow-up, the investigator or designee will make every effort to regain contact with the participant (where possible, 3 telephone calls and, if necessary, a certified letter to the participant's last known mailing address or local equivalent methods). These contact attempts will be documented in the participant's medical record or study file.
- We will use multiple methods to contact participants who drop out, including text messaging and/or email.
- Should the participant continue to be unreachable, he or she will be considered to have withdrawn from the study with a primary reason of lost to follow-up.

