8.3.3 CLASSIFICATION OF AN ADVERSE EVENT

8.3.3.1 SEVERITY OF EVENT

As part of the safety monitoring system, AEs reported to study staff at any time will be reviewed by the medical safety officer, who will identify, assess severity and relatedness to study drug, and if needed, manage the event. The study staff will report AEs and/or any unanticipated problems, to the medical safety officer. For AEs that require medical attention, the medical safety officer will directly contact the subject.

Safety related events will be reported within 10 days, as required by the SMC and the IRB that are responsible for study oversight.

For ongoing participant safety, events are assessed by the medical safety officer or Investigator to determine if they are Serious, Unexpected, or Related to study participation. If the event is reportable to the IRB, an event evaluation form will be completed that will include a description of the event, a classification of seriousness, assessment of potential relationship to the intervention, assessment of need for change in the consent or the study activities, a summary of known prior health issues, event outcome and a classification of the main organ system involved. The classification of potential relationship to the intervention is as follows.

Definite - Temporal pattern + Known or expected AE response pattern + Confirmed by stopping the intervention + Reappearance of AE on re-challenge

Probable - Temporal pattern + Known or expected AE response pattern + Confirmed by stopping the intervention + could not be explained by participant's clinical state

Possible - Temporal pattern + Known or expected AE response pattern + could have been produced by a number of other factors

Unknown - Relationship for which no evaluation can be made.

Not related - AE for which sufficient information exists to indicate that the cause is unrelated to the study intervention

The medical safety officer or the Investigator will determine the attribution/relatedness of each AE. The PI will report AEs to NINR every 6 months, including actions taken by the IRB as a result of such AEs.

See MOP chapter 12, Safety Monitoring and Serious Adverse Events, for more details of adverse and serious adverse events (SAEs) including the Study Medication Symptom Monitoring Form, the Adverse Event Form, and the Suicide Algorithm.

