8.3.4 TIME PERIOD AND FREQUENCY FOR EVENT ASSESSMENT AND FOLLOW-UP

The occurrence of an AE or SAE may come to the attention of study personnel during study visits and interviews of a study participant presenting for medical care.

All AEs, not otherwise precluded per the protocol, will be captured on the AE Form (included in MOP chapter 12, Safety Monitoring and Serious Adverse Events). Information to be collected includes event description, time of onset, clinician's assessment of severity, relationship to study procedures, and time of resolution/stabilization of the event. All AEs occurring while on study will be documented appropriately regardless of relationship. All AEs will be followed to adequate resolution or stabilization.

Any medical or psychiatric condition that is present at the time that the participant is screened will be considered as baseline and not reported as an AE. However, if the study participant's condition deteriorates at any time during the study, it will be recorded as an AE.

Changes in the severity of an AE will be documented to allow an assessment of the duration of the event at each level of severity to be performed. Documentation of onset and duration of each episode will be maintained for AEs characterized as intermittent.

Clinic staff and the study safety officer will record events with start dates occurring any time after informed consent is obtained. At each study visit, the investigator will inquire about the occurrence of AE/SAEs since the last visit. Events will be followed for outcome information until resolution or stabilization.

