9.2 SAMPLE SIZE DETERMINATION

With 280 participants and 20% loss to follow-up, we will have 75 evaluable participants in each treatment group. Based on published literature (*Kroenke K et. al JAMA July 2014*), the estimated standard deviation (SD) for BPI GPS score is 2.2. Assuming a moderate correlation of 0.5 between baseline and follow-up measures, we estimate that the SD in an analysis of covariance (ANCOVA) will be approximately 1.9. Therefore, we will have 90% power to detect a difference of -1 in BPI GPS score between combination groups (n= 150) and drug only group (n=75) for Aim 1. The power will be 83% power for comparison between combination with health care professional (n=75) and combination without health care professional (n=75) for Aim 2. All power calculations are based on two-sided t tests with alpha level of 0.025 to adjust for Bonferroni correction of testing two main hypotheses.

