10.4 PROTOCOL AMENDMENT HISTORY

The table below is intended to capture changes of IRB approved versions of the protocol, including a description of the change and rationale. A **Summary of Changes** table for the current amendment is located in the **Protocol Title Page**.

Version	Date	Description of Change	Brief Rationale
1	05/13/2020	IRB approved	Original version
2	12/08/2020	Protocol modified to NIH preferred format	NIH provided “NIH Protocol Template for Behavioral and Social Sciences Research Involving Humans”
3	12/17/2020	Protocol modified to include NIH suggested changes.	Response to NIH reviewers' feedback.
4	01/14/2021	At week 25, participants who would like to continue duloxetine will be prescribed a 2-week supply of duloxetine. Modified Table 1 to indicate Pre-Screening.	The 2-week supply will give participants enough time to ask their PCP for a refill. Modified Table 1 to indicate Pre-Screening.
5	03/11/2021	Change to the calculation of our primary outcome on Page 30.	Compared to the use of change score as the primary outcome, ANCOVA is generally superior in terms of efficiency, precision, and power. Therefore, the primary analysis will be Week 13 and 25 BPI scores as a primary outcome while adjusting for baseline measurement.
	04/14/2021	Changed “nurse” to “coach” throughout the protocol.	It was determined by speaking with the hiring department and nursing management that the coaching did not have to be done by a nurse. The Informed Consent document indicates “coach”.
	04/19/2021	Updated Table 1, footnote.	Made correction to footnote “e”: “At week 1, participants will receive duloxetine 60 mg once daily for 24 weeks”.
6	07/19/2021	Added footnote “i” to Table 1. Added text to Section 6.1.1. Added using text messaging as an adjunct to our phone calls to assess duloxetine symptoms monitoring at weeks 2 and 4 and for appointment reminders.	We have observed that a substantial proportion of participants perceive the phone calls as “burdensome”. This is manifested by not answering or not returning our calls. To address this issue, we have

			added the option of using text messaging as an adjunct to our phone calls.

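### No safety contact is scheduled after week 25, when participants still on duloxetine taper, stop from 30 mg or start a 2-week supply

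*Combined protocol and SAP*

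**What the plan says.** **Dosing from week 25.** The Synopsis and section 6.1.1 set three routes for participants still on duloxetine:

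- Stopping: "last study visit (week 25), participants who would like to stop the medication, will be provided duloxetine 30 mg once daily for 7 days"; treatment then ends.
- Already on 30 mg: dosing stops at the week 25 visit.
- Continuing: a 2-week supply is prescribed, the participant is told to speak to the PCP, and the investigator messages the PCP to consider continuing the drug.

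**Scheduled contacts.** Footnote a of Table 1 (section 1.3) says that the table lists the weeks with participant contact. Its last dated column is week 25, followed only by an as-needed column. Sections 6.1.1 and 8.2 place the Symptom Monitoring Form at weeks 1, 2, 4, 13 and 25. The Synopsis adds: "The time it will take for each individual participant to complete all study-related tasks is 25 weeks".

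**Adverse events.** Section 8.3.4 ties the investigator's AE question to study visits, and says that an event "may come to the attention of study personnel during study visits and interviews of a study participant presenting for medical care". It also says: "All AEs occurring while on study will be documented appropriately regardless of relationship". Section 8.3.3.1 says that "AEs reported to study staff at any time will be reviewed by the medical safety officer".

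**The recognised risk.** Section 2.3.1 gives prevention of discontinuation syndrome as the purpose of the 7-day taper.

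**The concern.** The protocol names a withdrawal risk, but its scheduled questions end before that risk can arise for anyone who follows the planned course to week 25. A participant who stops early remains in all later scheduled assessments (section 7.1). A participant who stops at week 25, as the plan provides, has none left.

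After week 25, a new symptom reaches the study only if the participant calls, seeks medical care or otherwise tells staff. The version 6 entry in section 10.4 describes participants who found the study's calls burdensome: "This is manifested by not answering or not returning our calls". That makes reliance on the participant to call first a weak safeguard.

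For those who continue, no step checks whether the drug was renewed. If it was not, the supply ends without a taper and without the study knowing.

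What is at stake is the safety of those participants and the completeness of the AE record that goes to the Safety Monitoring Committee and NINR. The efficacy question is not at stake.

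**Working it through.** **1. Reproduce the plan's own timeline.** One week at 30 mg plus 24 weeks at 60 mg: 1 + 24 = week 25. This agrees with the last visit and the stated duration.

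**2. Add the drug supplied at week 25** (Synopsis; section 6.1.1).

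| Route | Days of drug after week 25 | Last planned dose | Weeks of dosing after last scheduled form |
|---|---|---|---|
| Taper from 60 mg | 7 | 25 + 1 = week 26 | 1 |
| Stop from 30 mg | 0 | week 25 | 0 |
| 2-week supply | 14 | 25 + 2 = week 27 | 2 |

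For the first two routes, all of the time after stopping also lies beyond the last scheduled form.

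**3. Compare with the schedule.** The latest of weeks 1, 2, 4, 13 and 25 is week 25. Scheduled safety contacts after it: 0.

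**4. What remains after week 25.**

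- Calls started by the participant (Table 1, as-needed column and footnote g; the extracted table does not show reliably which row that footnote belongs to).
- Spontaneous reports and presentation for care (sections 8.3.3.1 and 8.3.4).
- Follow-up of events already open until they resolve or stabilise (section 8.3.4).
- The one-year record extraction, which counts referrals, visits and surgeries (section 9.4.9) and is not a participant contact.

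None of these asks a participant about a new symptom.

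**5. How many participants.** The ceiling is all 280. Section 9.2 states: "With 280 participants and 20% loss to follow-up, we will have 75 evaluable participants in each treatment group". Check: 280 × 0.80 = 224, and 224 / 3 = 74.7, or about 75 per group. So about 224 are expected at week 25. Some will already have stopped the drug; the documents do not say how many. If 10% to 40% have (an assumption without a source in the documents), 224 × 0.90 = 202 to 224 × 0.60 = 134 would still be on it.

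**6. Where a contact would fall.** Seven days after the last planned dose: 25 + 0 + 1 = week 26 (stop from 30 mg), 25 + 1 + 1 = week 27 (taper), 25 + 2 + 1 = week 28 (2-week supply).

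**The case against.** **The risk is already managed.** This is a Phase 4 trial of an approved drug. The taper is the mitigation, and those stopping from 30 mg are already at the taper dose. This stands, and it limits the weight of the point. A preventive measure does not show whether it worked, however, and nobody is scheduled to ask.

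**The hand-over is deliberate.** The version 4 log entry explains that two weeks gives participants time to request a refill, and the PCP is messaged. This also stands: a reader might infer that participants are left without a plan, and the text does not support that. What is missing is a check that the hand-over succeeded.

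**Late events might seem out of scope.** Because section 8.3.4 speaks of events while on study and the stated duration is 25 weeks, a reader might infer that an event at weeks 26 to 28 would not be recorded. The documents do not support this. Section 8.3.3.1 accepts reports at any time, and section 8.3.4 records events starting any time after consent, with no cut-off. The gap is in active asking, not in eligibility for recording.

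**The trial result might seem affected.** It is not. All three arms receive duloxetine, the primary outcome is measured at weeks 13 and 25, and no safety analysis is planned (section 9.4.4).

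**The MOP may hold the contact.** Chapters 09 and 12 are cited but were not available for this review. Table 1 is marked as revised 07/19/2021, before version 8 (11/01/2022) clarified the end-of-study drug procedure, so it may not be complete. This stands, and the recommendation is conditional on it.

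**Conclusion.** The point holds for the protocol as written. There are no scheduled safety contacts after week 25, while planned dosing runs 7 days longer on the taper, 14 days longer on the 2-week supply, or stops at the visit from 30 mg.

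This is a cheap improvement in safety capture. It is not an error that threatens the trial's conclusions.

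The documents give no frequency of withdrawal symptoms or of failed renewal, so neither the number of missed events nor the size of any undercount can be estimated. Nor can one say how many participants could still benefit: that depends on accrual, which is not given, and anyone already past week 25 is beyond reach. The figure of 224 at week 25 rests on the planned 20% loss; 134 to 202 still on drug rests on the assumption stated above.

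**What to change.** For each participant still on duloxetine at week 25, add one symptom check by text or phone, the channels already used at weeks 2 and 4.

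- **Timing:** about 7 days after the last planned dose (about week 26, 27 or 28 by route), with the interval confirmed by the medical safety officer.
- **Content:** withdrawal symptoms, and whether duloxetine was stopped or continued. The items on the existing Symptom Monitoring Form are not shown, so these questions may have to be added.
- **Attempts:** up to three, in line with section 7.3, where loss to follow-up requires a missed in-person visit and that "study staff are unable to contact the participant after at least 3 attempts".
- **Text:** list the contact in Table 1 and section 8.2, update the participant duration, and state in section 8.3.4 that active AE collection runs to that contact. If the MOP already holds it, list it in Table 1.
- **Accompanying editorial correction:** align Table 1 footnote f, which gives everyone the taper, with the three routes in section 6.1.1. This adds no weight to the main point.

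Leave the primary endpoint at week 25 and the taper as it is.

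**Cost.** Protocol and consent wording, and one short contact per participant on drug: 280 at the very most, and fewer in practice. Assume 5 to 15 minutes per completed contact plus two unanswered attempts of 3 minutes each, so 11 to 21 minutes. Then 134 × 11 / 60 = 25 hours to 202 × 21 / 60 = 71 hours over the trial, with a ceiling of 280 × 21 / 60 = 98 hours. Any new consent of current participants is extra. Some participants will not respond.

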1.2 SCHEMA

Flow Diagram

1.3 SCHEDULE OF ACTIVITIES

Table 1. Study Measures and Time Points for Data Collection in PRECICE

Telephone Contacts/Visits ^a	Pre-Screening Visit	Week 0	Week 1	Week 2	Week 3	Week 4	Week 6	Week 10	Week 13	Week 14	Week 18	Week 22	Week 25	PRN
Type of Contact/Visit ^{b,c}	TC	IPV	IPV	TC	TC	TC	TC	TC	IPV	TC	TC	TC	IPV	PRN
Screening														
Phone Pre-Screening	✓													
Randomization			✓											
Physical Measures														
Blood Pressure	✓	✓							✓				✓	
Height	✓												✓	
Weight	✓												✓	
Urine Pregnancy Test	✓								✓					
Questionnaires														
3-item Pain Intensity Interview	✓								✓				✓	
Compiled Questionnaires		✓							✓				✓	
o Brief Pain Inventory														
o Generalized Anxiety Disorder (GAD-7)														
o Patient Health Questionnaire (PHQ8)														
o Global Rating of Change (GRoC)														
o Pain Catastrophizing Scale (PCS)														
o PROMIS Adult Self-Report														
o Chronic Pain Coping Inventory (CPCI)														
Demographics with Medical Diagnosis		✓												
Informed Consent		✓												
Missed Visit Form													✓	
Modified Pain Detect	✓													
Non-study Medication List	✓								✓				✓	
Nurse Counselling Tracking Form						✓		✓	✓		✓	✓	✓	
Opioid Risk Tool	✓													
Participant Status													✓	
Serious Adverse Event Report Form													✓	
Study Drug Accountability Log	✓ ^d	✓ ^e								✓			✓ ^f	
Study Medication Modification				✓						✓			✓ ^g	
Study Medication Symptom Monitoring Form		✓ ^h	✓ ⁱ			✓ ⁱ			✓ ⁱ		✓		✓ ^j	
TAPS – Tobacco, Alcohol, Prescription	✓												✓	
EMR Health Care Utilization ^h														

^a Weeks with participant contact are listed on this table.

^b IPV indicates in-person visit.

^c TC indicates telephone contact.

^d At study entry, all participants will receive duloxetine 30 mg once daily for one week.

^e At week 1, participants will receive duloxetine 60 mg once daily for 24 weeks.

^f At week 25, all participants will be provided duloxetine 30 mg once daily for 7 days and medication treatment will then stop (tapering regimen).

^g Phone administration on as needed basis only if participant calls the research office and complains of a potential side effect.

^h EMR Health Care Utilization will be collected at one year after randomization.

ⁱ Option of using text messaging as an adjunct to phone calls to assess duloxetine symptoms monitoring at weeks 2 and 4.

Revised 07/19/2021

